## 8.2 Primary Objective

### 8.2.1 Outline of Approach

The primary objective is to determine the utility of the Disease Severity Index (DSI), derived from the HepQuant SHUNT test, for monitoring liver disease and treatment effects.

- Utility will be defined by measuring DSI and the change in DSI ( $\Delta$ DSI) across all treatment arms.
- The clinical significance of a change in DSI will be evaluated by analyzing the relationships between changes in DSI and changes in histologic stage of disease, clinical models, and risk for clinical outcome.

Treatment effect will be determined after the completion of the clinical trial and after completion of Gilead's analysis of the results of the main clinical trial. Treatment effect will be defined from the difference in  $\Delta$ DSI between treatment and placebo arms. Treatment effect defined by  $\Delta$ DSI will also be compared to the treatment effect defined by changes in other tests and by clinical outcomes.

### 8.2.2 Comparators from the Gilead Clinical Trials

The primary clinical or histologic outcomes for the Gilead Clinical Trials are:

- STELLAR 3:
  - Wk48: Decrease fibrosis stage  $\geq 1$ ; no worsening NASH
  - Wk48: Freedom from progression to cirrhosis
  - Wk48: Freedom from decompensation, transplant, death
  - Wk240: Decrease fibrosis stage  $\geq 1$ ; no worsening NASH
  - Wk240: Freedom from progression to cirrhosis
  - Wk240: Freedom from decompensation, transplant, death
  
- STELLAR 4:
  - Wk48: Decrease fibrosis stage  $\geq 1$ ; no worsening NASH
  - Wk48: Freedom from decompensation, transplant, death
  - Wk240: Decrease fibrosis stage  $\geq 1$ ; no worsening NASH
  - Wk240: Freedom from decompensation, transplant, death
  
- GS-US-454-4378 (F3):
  - Wk48: Decrease fibrosis stage  $\geq 1$ ; no worsening NASH
  - Wk48: Freedom from progression to cirrhosis
  - Wk48: Freedom from decompensation, transplant, death
  
- GS-US-454-4378 (F4):
  - Wk48: Decrease fibrosis stage  $\geq 1$ ; no worsening NASH
  - Wk48: Freedom from decompensation, transplant, death

The definition of worsening of NASH is a  $\geq 1$  point increase in hepatocellular ballooning or lobular inflammation using histologic criteria of the NASH CRN.

### 8.2.3 Statistical Considerations

Our Primary Objective is to determine the utility of the Disease Severity Index (DSI), derived from the HepQuant SHUNT test, to monitor liver disease and treatment effects. We propose a three-step analytical process to achieve this goal:

- First, without knowledge of treatment arm and for the group of subjects as a whole, we will track DSI and the change in DSI,  $\Delta$ DSI, from baseline to on-treatment and follow-up timepoints.
- Second, we will apply separate survival models to evaluate  $\Delta$ DSI as a continuous variable and a 2 point or more drop in DSI as dichotomous variable in the prediction of changes in other tests or models of liver disease severity and clinical outcomes.
- Third, after unblinding the study and completion of Gilead's analysis of the main clinical trial, we will make request of Gilead for allocation code to determine if there is a treatment effect, by comparing the difference between the  $\Delta$ DSI of the treatment arm versus the  $\Delta$ DSI of the placebo arm. The significance of this difference will be evaluated using two-sided t-tests and survival models.

Due to short enrollment period, only 5 STELLAR 3 and 4 STELLAR 4 subjects were enrolled into HQ-SHUNT-1701. STELLAR 3 and STELLAR 4 had two treatment arms (6 and 18 mg/d doses) and one placebo arm. Of the 9 subjects enrolled in HQ-SHUNT-1701, we would project that 6 would have been treated with selonsertib and 3 would have been taking placebo. Enrollment criteria, diagnosis, and F3/F4 stage of NASH is identical between the STELLAR studies and Gilead 454-4378. For the final analysis of treatment effects, once the code on all treatment arms from all studies is unblinded the projected 6 cases enrolled in HQ-SHUNT-1701 on selonsertib treatment from STELLAR studies will be added to the cases from Arm C of 454-4378 (selonsertib monotherapy) and the projected 3 cases enrolled in HQ-SHUNT-1701 on placebo from STELLAR studies will be added to the cases from Arm F (placebo) of the 454-4378 study.

Furthermore, we will link treatment effect defined by the change in DSI to effects of treatment on other tests and clinical outcomes (bleeding from varices or portal hypertensive gastropathy, ascites, encephalopathy, SBP, progression to cirrhosis, and

patient mortality or liver transplantation). In addition, we will use both generalized estimating equations (GEE) and profile analysis – profile of DSI between treatment and placebo groups at each time point – for additional primary endpoint analyses. The two NASH trials will be combined in the analysis of treatment effect.

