### 2.1 Primary Objective

The primary objective is to determine the utility of the Disease Severity Index (DSI) derived from the HepQuant SHUNT test, which measures liver function and physiology, for monitoring liver disease and treatment effects.

- Utility will be defined by measuring DSI and the change in DSI ( $\Delta$ DSI) across all treatment arms. DSI and  $\Delta$ DSI will be evaluated in real time.
- The clinical significance of changes in DSI will be evaluated by analyzing the relationship of  $\Delta$ DSI to changes in histologic stage of disease, standard laboratory tests, clinical models, or risk for clinical outcome. Some of the proposed comparative analyses will only be performed after unblinding of treatment arms and completion of analyses for the main Gilead trials and may be conducted by Gilead.
- Treatment effects will only be determined after unblinding the treatment arms and completion of the analyses for the main Gilead trials. In terms of DSI, treatment effects will be determined from the differences in DSI and  $\Delta$ DSI between treatment and placebo arms. The analyses will be conducted by Gilead.

**Clinically-meaningful outcomes.** As noted above, the subjects will be followed for clinical outcomes in the Gilead trials. In the case of STELLAR 3 and 4, the follow-up for clinical outcomes (bleeding from varices or portal hypertensive gastropathy, ascites, encephalopathy, liver-related death) will be up to 240 Wks – the  $\Delta$ DSI associated with development of clinical outcome at both Wk48 and Wk240 will be analyzed. In the case of GS-US-454-4378, the follow-up for clinical outcomes will be for 48 Weeks.

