## **8.0 Data Analysis and Statistics**

### **8.1 Sample Size Calculation**

An important offshoot of our prior serial studies of the HepQuant SHUNT test was defining an average standard deviation for  $\Delta$ DSI (average SD of  $\Delta$ DSI = 3.5) that could

be used to determine sample sizes. The following table demonstrates the sample sizes required to detect a range of changes in DSI at 80% power or higher – for the case of the NASH trials. A sample size of 60 total subjects (N in following table), well below the size of our projected number of evaluable NASH patients could provide sufficient power to detect a difference in the  $\Delta$ DSI of 2 to 3.

Actual Power	N1	N2	N	<math>\Delta</math>DSI	<math>\sigma</math>	Alpha
0.80010	112	112	224	1.00	3.00	0.050
0.80084	199	199	398	1.00	4.00	0.050
0.80590	29	29	58	2.00	3.00	0.050
0.80590	51	51	102	2.00	4.00	0.050
0.82409	14	14	28	3.00	3.00	0.050
0.80486	23	23	46	3.00	4.00	0.050
0.81316	8	8	16	4.00	3.00	0.050
0.82409	14	14	28	4.00	4.00	0.050
0.85055	6	6	12	5.00	3.00	0.050
0.81383	9	9	18	5.00	4.00	0.050
0.80153	4	4	8	6.00	3.00	0.050
0.84086	7	7	14	6.00	4.00	0.050

NOTE: Once the treatment for the clinical trial is unblinded, if DSI is unchanged or worsens by 1 in the placebo arm, then one could detect as little as a 1 or 2 point reduction in DSI by selonsertib in the treatment arm.

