### **8.3.3 Baseline DSI as a predictor of Clinical Outcome**

Our goal is to correlate the baseline DSI with risk for clinical outcomes. The primary clinical outcomes in the Gilead clinical trials include:

- STELLAR 3: Wk48: Decrease fibrosis stage  $\geq 1$ ; no worsening NASH  
Wk48: Freedom from progression to cirrhosis  
Wk48: Freedom from decompensation, transplant, death  
Wk240: Decrease fibrosis stage  $\geq 1$ ; no worsening NASH  
Wk240: Freedom from progression to cirrhosis  
Wk240: Freedom from decompensation, transplant, death
- STELLAR 4: Wk48: Decrease fibrosis stage  $\geq 1$ ; no worsening NASH  
Wk48: Freedom from decompensation, transplant, death  
Wk240: Decrease fibrosis stage  $\geq 1$ ; no worsening NASH  
Wk240: Freedom from decompensation, transplant, death
- GS-US-454-4378 (F3): Wk48: Decrease fibrosis stage  $\geq 1$ ; no worsening NASH  
Wk48: Freedom from progression to cirrhosis  
Wk48: Freedom from decompensation, transplant, death
- GS-US-454-4378 (F4): Wk48: Decrease fibrosis stage  $\geq 1$ ; no worsening NASH  
Wk48: Freedom from decompensation, transplant, death

We will perform survival analysis for freedom from clinical outcome by Kaplan-Meier plots. Cox models will be used to estimate hazard ratios corresponding to 1 unit of DSI, controlling for other known risk factors of mortality (age, gender, smoking, etc). We will also apply separate survival models to evaluate DSI as a continuous variable and as above or below mean DSI as dichotomous variable in the prediction of clinical outcomes. In a secondary analysis of the combined NASH trials, we will use a discriminant analysis to compare the ability of baseline DSI to the ability of other tests and models to predict clinical outcomes.

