## 9.0 Summary

This HepQuant study, conducted in parallel with three Gilead clinical trials, will determine the utility of DSI scores derived from the HepQuant SHUNT test for monitoring liver disease and treatment effects by measuring liver function and physiology. The results of DSI may be linked by Gilead to clinically meaningful changes in histology, laboratory tests, clinical models, and patient clinical outcomes. No more than 100 subjects will be

studied. The proposed HepQuant study and analytical plan will specifically measure the ability of DSI and  $\Delta$ DSI to:

1. Define baseline disease severity, and
2. Detect clinically-meaningful changes in DSI by relating them to:
  - a. changes in histology,
  - b. changes in laboratory tests,
  - c. changes in clinical models, and
  - d. risk for clinical outcome.

The performance of DSI relative to other measurements made in these clinical trials could potentially establish DSI as an important tool for monitoring liver disease and treatment effects.

The HepQuant study will address key issues in NASH – is HepQuant SHUNT suitable for defining severity of the liver disease and monitoring the response of the liver to NASH treatment?

- The comparison of  $\Delta$ DSI to change in NASH CRN fibrosis stage could provide evidence that supports use of  $\Delta$ DSI as a potential surrogate for assessing changes in fibrosis stage – i.e., using  $\Delta$ DSI as a minimally-invasive alternative to biopsy for monitoring treatment effects.
- Examining the baseline heterogeneity in functional impairment in NASH might identify high and low risk subgroups with different treatment response or clinical outcomes (such as progression to cirrhosis, or risk for clinical outcomes).
- Comparing the  $\Delta$ DSI of the treatment arms to the  $\Delta$ DSI of the placebo arm will demonstrate the effect of treatment. Not only baseline DSI but also  $\Delta$ DSI will be correlated to the other tests, clinical models, and clinical outcomes. Changes in individual parameters of the HepQuant SHUNT test may identify the specific hepatic effects of the treatment.

Overall, the results from this study may support the use of HepQuant SHUNT as a tool or even endpoint for assessing efficacy of drug therapy of fibrotic stages of NASH in future trials.

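### The models relating change in DSI to outcome state no treatment term and no refit by arm after unblinding, so the association meant to support a surrogate claim may be modestly inflated

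*Combined protocol and SAP*

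**What the plan says.** Section 8.2.3 sets out three steps.

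- **Step 1** follows DSI and its change over time "without knowledge of treatment arm and for the group of subjects as a whole". It fits no outcome model.
- **Step 2** fits separate survival models with change in DSI "as a continuous variable and a 2 point or more drop in DSI as dichotomous variable", to predict changes in other tests or models of severity and clinical outcomes. It does not mention treatment.
- **Step 3** requests the allocation code after unblinding and compares change in DSI between arms, by two-sided t-tests and survival models.

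The section then adds that "we will link treatment effect defined by the change in DSI to effects of treatment on other tests and clinical outcomes", and names GEE and a profile analysis of DSI by group.

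On timing, Section 2.1 says: "Some of the proposed comparative analyses will only be performed after unblinding of treatment arms and completion of analyses for the main Gilead trials". It adds that the parent-trial sponsor may conduct them.

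The only covariates named for any outcome model are in Section 8.3.3, for the baseline-DSI Cox models: "controlling for other known risk factors of mortality (age, gender, smoking, etc"). Treatment is not listed by name.

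Section 9.0 says that comparing change in DSI with change in fibrosis stage could support its use "as a potential surrogate for assessing changes in fibrosis stage" and "as a minimally-invasive alternative to biopsy for monitoring treatment effects".

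**The concern.** The subjects come from randomised placebo-controlled trials, and Section 2.1 expects effective treatment to lower DSI. If a drug also improves histology, treatment is a common cause of both. Across arms together, subjects with larger DSI drops would then show more histologic improvement simply because more of them received active drug. A pooled model cannot separate this from DSI following disease in the individual subject.

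The distinction matters for the claim in Section 9.0. Replacing a biopsy in monitoring requires that change in DSI be informative about change in fibrosis among subjects on the same treatment. The plan does not state an analysis that estimates this.

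**Working it through.** **The plan's own figures.** The plan gives no figure for this association. Its only calculation, the table in Section 8.1, concerns the between-arm difference. The row "0.80590 29 29 58 2.00 3.00 0.050" (29 per arm, difference 2, SD 3) is reproduced exactly by a noncentral-t calculation at one-sided 0.05. Two-sided power is 0.704. That mismatch is a separate matter and is not used below.

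**Inputs**

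- N = 100, the cap (Synopsis, Section 5.1). N = 60, from Section 8.1, is a second case.
- SD of change in DSI = 3.5 (Section 8.1).
- Between-arm DSI shift d = 2 to 3 points, the range that Section 8.1 says 60 subjects could detect.
- Response p1 = 0.43 (13/30, selonsertib 18 mg with or without simtuzumab) and p0 = 0.20 (2/10), from the Phase 2 table in Section 3.2.1. The comparator is simtuzumab alone, not placebo, so these rates are illustrative.
- Active share π. Section 8.2.3 projects 6 active and 3 placebo among the 9 STELLAR subjects, or 2:1. The split in GS-US-454-4378 is not stated. Section 8.2.3 mentions Arms C and F. If there were six equal arms (an assumption), 91 subjects would give 91 × 5/6 = 75.8 active. Adding 6 gives 81.8 of 100, or about 82:18. I use 82:18 to 2:1.
- Within each arm, change in DSI and outcome are independent. All active arms are treated as one.

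**Formula.** With q = π(1 − π) and p̄ = πp1 + (1 − π)p0, the correlation created by pooling alone is

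r = q·d·(p1 − p0) / [√(SD² + q·d²) · √(p̄(1 − p̄))].

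**At 2:1, d = 2.** q = 0.2222 and p̄ = 0.3533. The numerator is 0.2222 × 2 × 0.23 = 0.1022. The denominator is √13.139 × √(0.3533 × 0.6467) = 3.625 × 0.478 = 1.733. So r = 0.059.

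**At 82:18, d = 2.** q = 0.1476 and p̄ = 0.3886. The numerator is 0.0679. The denominator is 3.583 × 0.487 = 1.746. So r = 0.039.

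**False-positive rate.** The normal approximation is Φ(z − 1.96) + Φ(−z − 1.96), with z = atanh(r)·√(N − 3) and N = 100. The simulated rates come from 20,000 datasets per scenario, using a linear association test in place of the survival model.

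| Split | d | r | Approximation | Simulated |
|---|---|---|---|---|
| 82:18 | 2 | 0.039 | 6.7% | about 7% |
| 82:18 | 3 | 0.057 | 8.7% | about 9% |
| 2:1 | 2 | 0.059 | 9.0% | 8.9% |
| 2:1 | 3 | 0.085 | 13.4% | 12.8% |

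At N = 60 and 2:1 the simulated rates are 7.3% (d = 2) and 10.2% (d = 3).

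**The dichotomy (2:1, d = 2, no mean change on placebo).** The chance of a drop of 2 or more is 0.500 on active and 1 − Φ(2/3.5) = 0.284 on placebo.

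- Overall chance of such a drop: 2/3 × 0.500 + 1/3 × 0.284 = 0.428.
- Response with a drop: (2/3 × 0.500 × 0.43 + 1/3 × 0.284 × 0.20) / 0.428 = 37.9%.
- Response without: (0.3533 − 0.1623) / 0.572 = 33.4%.
- Spurious odds ratio: 1.22.

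**Checks.** If d = 0 or p1 = p0, the formula gives r = 0 and the simulated rate stays near 5%. With an arm term in the model, the simulated rate was 4.7% to 5.3% in every scenario.

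**The case against.** The strongest reply is that this is silence rather than a stated choice. The phrase about not knowing the treatment arm belongs to step 1, which only tracks DSI. Step 2 does not itself say that its models are blinded, pooled or unadjusted. Sections 1.1.3, 5.3.2 and 5.3.3 give the analyses against other trial data to the parent-trial sponsor under a collaborative agreement that is not in the documents, and Section 2.1 places some of them after unblinding. All of this stands. A reader might infer that the plan rules out adjusting for treatment, but the documents support only that no adjustment or refit is stated. Pooling in step 2 is an inference from the order of the steps and the absence of any mention of arm.

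A reader might also infer that a drug effect could make DSI look like a convincing surrogate. The figures do not support this. The largest correlation in the table, 0.085, explains 0.7% of variance. Much larger distortion needs inputs that do not fit this study. A 4.4-point shift with response 60% v 15% gives about 59% false positives at 2:1. However, 4.4 points is a week-4 change within a subgroup of hepatitis C transplant recipients (Section 3.1.9), and those response rates have no source in the documents. Equal allocation (d = 3: r 0.098, 16%) conflicts with the two active arms and one placebo arm in STELLAR and with the several active regimens in GS-US-454-4378.

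Finally, Section 9.0 is hedged, and agreement between arms is itself informative about monitoring treatment effects. That argues for reporting both estimates, not for leaving out the adjusted one.

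**Conclusion.** The point holds in a limited form. Step 2 states no treatment term or within-arm analysis, precedes the request for the allocation code, and is not said to be refitted afterwards. The association given treatment, which the surrogate idea in Section 9.0 needs, is therefore left unspecified.

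Under the illustrative inputs the inflation is real but modest: an induced correlation of about 0.04 to 0.09, and false positives of about 7% to 13% instead of 5%. It arises only if treatment moves both DSI and the outcome. The size rests on N at its cap, Phase 2 response rates without a placebo comparator, an unstated allocation split, active arms combined into one, no dropout, and a simple association test in place of the planned survival models.

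**What to change.** Add to step 3 of Section 8.2.3 that, after unblinding, each step 2 model is refitted with treatment as a covariate or stratum: active v placebo, or individual arm where numbers allow. Report this estimate beside the pooled one, and base any statement about DSI as a surrogate on the treatment-adjusted estimate. Add fibrosis stage or parent trial only where numbers allow, since STELLAR contributes 9 subjects.

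The cost is one extra model per outcome and slightly wider intervals. Models with few events may not support the extra term, and where that happens the report should say so. The allocation code is already to be requested, but the parent-trial sponsor holds the outcome data, so the refit has to be included in the analyses requested from it.

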**Statistical Methods:**

We will determine the utility of the Disease Severity Index (DSI) from the HepQuant SHUNT test to monitor liver disease and treatment effects by measuring liver function and physiology. We propose a three-step analytical process to achieve this goal. First, without knowledge of treatment arm, we will track DSI and the change in DSI,  $\Delta$ DSI, from baseline to on-treatment and follow-up timepoints. Second, we will apply separate survival models to evaluate  $\Delta$ DSI as a continuous variable and a 2 point or more change in DSI as dichotomous variable in the prediction of changes in other tests or models of liver disease severity and clinical outcomes. In HCV, an increase in DSI of 2 or more has been associated with disease progression; and, a decrease in DSI of 2 or more has been associated with improvement after viral clearance. Third, once the treatment arms have been unblinded we will evaluate if the use of the HepQuant SHUNT test and DSI identify a treatment effect in the combined cohort of NASH F3 plus NASH F4; and we will compare DSI to the primary measures of efficacy in each of the clinical trials. In terms of DSI, a treatment effect will be defined from the difference between the  $\Delta$ DSI of the treatment arm versus the  $\Delta$ DSI of the placebo arm. The significance of this difference will be evaluated using a two-sided t-test. Furthermore, we will link treatment effect defined by DSI to effects of treatment on other tests and clinical outcomes (bleeding from varices or portal hypertensive gastropathy, ascites, encephalopathy, SBP, progression to cirrhosis, and patient mortality or liver transplantation). We will use both generalized estimating equations (GEE) and profile analysis – profile of DSI between treatment and placebo groups at each time point – for additional primary endpoint analyses.

We will also determine the ability of baseline DSI, performed prior to treatment, to assess the severity of liver disease by: 1. correlation with other baseline tests of liver disease severity; and, 2. prediction of risk for future clinical outcome.

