## 1.2 Rationale for Conducting this Study

Why conduct this research study? There is an unmet medical need for a non-invasive or minimally-invasive test that accurately measures liver function and physiology. The HepQuant SHUNT Test is minimally-invasive and measures hepatocyte function and inflow to the liver from the simultaneous clearances (hepatic filtration rates, HFRs) of cholate from systemic and portal circulations. The Test quantifies portal-systemic shunting (SHUNT) and generates a liver disease severity index (DSI) [1]. DSI is a score from 0 (no disease) to 50 (terminal illness) that is a composite of both HFRs and correlates with stage of fibrosis, presence of varices, especially large varices, and risk for future clinical outcomes [2-8]. DSI is the primary output variable from the HepQuant SHUNT test. The HepQuant SHUNT test potentially satisfies the unmet medical need for a minimally-invasive test of global liver function and physiology.

HepQuant believes that DSI from baseline and serial HepQuant SHUNT tests will be useful in defining baseline disease severity and that the change in DSI,  $\Delta$ DSI, will detect clinically meaningful changes in liver disease and responses to treatment.

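### Step 2 relates ΔDSI to clinical outcomes without baseline DSI in the model, so it cannot show whether serial testing adds to the baseline test

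*Combined protocol and SAP*

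**What the plan says.** Section 8.2.3 sets out three steps for the primary objective. In the second, separate survival models take two predictors in turn. The section writes a delta sign in front of the first: "DSI as a continuous variable and a 2 point or more drop in DSI as dichotomous variable". Each is to serve as a "variable in the prediction of changes in other tests or models of liver disease severity and clinical outcomes". The synopsis has the same step ("we will apply separate survival models to evaluate") but defines the class as a change rather than a drop: "DSI as a continuous variable and a 2 point or more change in DSI as dichotomous variable". Neither place names baseline DSI, or any other covariate, for these models.

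Baseline DSI is related to outcome under the secondary objective. Section 8.3.3 states that "Cox models will be used to estimate hazard ratios corresponding to 1 unit of DSI". The adjustment terms named there are age, gender and smoking, in a list left open; ΔDSI is not among them. The Summary (section 9.0) says that both baseline DSI and ΔDSI will be correlated with other tests and outcomes, but no section puts them in one model. The GEE and profile analyses at the end of section 8.2.3 compare DSI between treatment and placebo groups, which is a different question.

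On the meaning of the level, section 1.2 says that "DSI is a score from 0 (no disease) to 50 (terminal illness") and that it correlates with fibrosis stage, varices and the risk of later outcomes. Section 3.1.8 says that DSI predicted cirrhosis, varices and clinical outcome in hepatitis C.

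**The concern.** If the level of DSI carries risk, then risk at a follow-up visit depends on where the subject started as well as on how far the score moved. A model with ΔDSI as the only DSI term cannot separate the two. A fall from 30 to 27 and a fall from 10 to 7 both give ΔDSI = −3 and both count as a two-point drop. Both step 2 predictors therefore score them alike, although current DSI differs by 27 − 7 = 20 points on a 50-point scale. (The documents give no DSI range for F3 or compensated F4 NASH, so these values only illustrate.)

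Two things are at stake for clinical outcomes. First, the ΔDSI coefficient can be biased by its correlation with baseline, in either direction. Second, the primary objective is monitoring, which asks whether a second test tells more than the first. Neither a ΔDSI-only model nor a baseline-only model answers that.

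**Working it through.** **Inputs.** SD of ΔDSI 3.5 (section 8.1). SOLAR-1 week 4 results (section 3.1.9): ΔDSI −4.4 ± 3.7, −1.7 ± 2.5 and 0.2 ± 2.8 in non-cirrhotic recipients, recipients with cirrhosis and decompensated non-transplant subjects; I read ± as SD, which the section does not state. The documents give no SD of baseline DSI, no test error, and no event count or power for step 2, so there is no planned figure to reproduce. Values marked as assumed are mine.

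**1. What the joint model estimates.** Let B be baseline DSI, F follow-up DSI and Δ = F − B. Then

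β_B·B + β_Δ·Δ = (β_B − β_Δ)·B + β_Δ·F.

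The ΔDSI coefficient given baseline is the follow-up coefficient given baseline, that is, the added value of the second test.

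**2. Bias of ΔDSI alone for a clinical outcome.** Suppose the log hazard rises by β per point of current DSI. To a linear approximation, the ΔDSI-only slope is β × [1 + cov(B, Δ)/var(Δ)].

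- Assumed equal SD s at both visits with correlation ρ: cov(B, Δ) = −s²(1 − ρ) and var(Δ) = 2s²(1 − ρ). The factor is 1 − 1/2 = 0.5, so a hazard ratio of 1.2 shrinks to about √1.2 = 1.10.
- True change unrelated to baseline and no test error: the covariance is 0 and the factor is 1, so there is no bias of this kind.
- Sicker subjects changing less favourably, as the SOLAR-1 group means suggest (transplant status also differs between those groups): the covariance is positive, the factor exceeds 1, and the association is overstated.

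Simulated Cox models for the first case (6,000 subjects, 15% with events, ρ = 1 − 3.5²/(2s²)):

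| s (assumed) | ρ | True HR per point | ΔDSI only | ΔDSI given baseline |
|---|---|---|---|---|
| 3.5 | 0.50 | 1.1 | 1.054 | 1.099 |
| 5 | 0.76 | 1.1 | 1.042 | 1.095 |
| 8 | 0.90 | 1.1 | 1.047 | 1.091 |
| 3.5 | 0.50 | 1.2 | 1.091 | 1.208 |
| 5 | 0.76 | 1.2 | 1.078 | 1.172 |
| 8 | 0.90 | 1.2 | 1.085 | 1.201 |

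**3. Outcomes that are themselves changes.** Take an error model in which the whole SOLAR-1 spread of 2.8 is test error (assumed). Error variance per test is v = 2.8²/2 = 3.92. True-change variance is c = 3.5² − 2 × 3.92 = 12.25 − 7.84 = 4.41. True change is unrelated to baseline, and the between-subject SD is 3, 5 or 8 (assumed). The share of variance in true change explained is:

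- ΔDSI alone: 4.41/12.25 = 36%.
- With baseline, c(s² + v)/[(s² + v) × 12.25 − v²]: for s = 3, 4.41 × 12.92/(12.92 × 12.25 − 15.37) = 40%; for s = 5, 38%; for s = 8, 37%.

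Omitting baseline costs little here.

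**4. The joint coefficient when nobody changes.** Keep v = 3.92, set true change to zero for all, and let the outcome follow the true level. The ΔDSI-only slope is 0. The joint ΔDSI slope is s²/(2s² + v): 9/21.92 = 0.41, 25/53.92 = 0.46 and 64/131.92 = 0.49. Measurement error alone makes it non-zero, because a second noisy reading improves the estimate of the level.

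**5. Room for a second term.** At most 100 subjects are planned. Section 2.2 expects clinical outcomes to develop slowly. Only 5 + 4 = 9 STELLAR subjects were enrolled, and only the STELLAR schedule runs to Week 240.

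**The case against.** **The omission is read from silence.** In step 2 the word separate divides the continuous from the dichotomous form of ΔDSI; it does not rule out covariates. DSI level is also tracked in step 1 and modelled in section 8.3.3. This stands in part: the plan does not forbid adjustment. But it names covariates for the baseline models and none for step 2, and it joins the two DSI terms nowhere.

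**Many step 2 outcomes are changes.** Changes in other tests or models come first in the step 2 sentence, and section 8.2.2 lists a fall in fibrosis stage for every trial. This stands, and item 3 of the working bears it out. The point is therefore confined to clinical outcomes.

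**The joint coefficient can mislead.** This stands too (item 4), and it rules out making the joint model the only evidence or demoting the ΔDSI-only model to a footnote.

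**A stronger reading is tempting:** that leaving out baseline discards most of the information. Under the error model of item 3, ΔDSI alone explains 12%, 5% or 2% of the variance of true current DSI (SD 3, 5, 8), against 81%, 91% or 96% with baseline added. The documents do not support that conclusion. Current DSI is not a step 2 outcome, and the high joint figures are close to an identity, since baseline plus change is the follow-up value. The figures also rest on an assumed between-subject SD and on treating all the spread in decompensated hepatitis C subjects as test error. With no test error, ΔDSI alone gives 58%, 33% or 16%.

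**Events may be too few for two terms.** This stands, and the fix has to provide for it.

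**Conclusion.** The point holds for the clinical-outcome models of step 2. As written, they give equal changes the same predicted risk whatever the starting level, they can understate or otherwise confound the association, and they leave the monitoring question unanswered. The first and third of these follow from the model form and the protocol's own premise that level predicts outcome.

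The size is uncertain. Roughly halving the log hazard ratio, as in the table, assumes that hazard follows current DSI and that the two visits have equal SDs. Under other assumptions the bias is nil or runs the other way. For outcomes that are changes in other tests the loss is small, and no correction is needed on this ground. The plan should be amended, but the gap does not invalidate step 2 as a whole.

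**What to change.** In section 8.2.3 and the synopsis, for clinical outcomes only, pre-specify a model with baseline DSI and continuous ΔDSI together (equivalently baseline plus follow-up DSI). Report the conditional ΔDSI coefficient with its 95% CI beside the ΔDSI-only result. State that the joint coefficient measures what the second test adds to the first and is not by itself proof that change is meaningful, because measurement error can produce it. List the step 2 covariates, even if baseline DSI is the only one, and reconcile drop with change in the two definitions of the two-point class.

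Set in advance the number of events below which the joint model is reported as descriptive. Include the model in the analyses requested from the drug-trial sponsor, since section 1.1.3 leaves the correlation analyses to that sponsor.

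The cost is some wording and one degree of freedom. No new data are needed, since every subject with a ΔDSI has a baseline DSI. The degree of freedom matters with at most 100 subjects, slow outcomes and 9 STELLAR subjects on the 240-week schedule.
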